Our objective is to develop personalized treatment approaches to the treatment of acute HF. The central hypothesis is that BVA will allow improved congestion phenotyping of acute HF patients given the ability to directly and accurately measure blood volume. Knowledge of specific congestion phenotypes will be the basis for targeted treatment algorithms. **The specific objectives are:**

Perform a pragmatic randomized pilot study (N=50) with blood volume analysis (BVA) – guided treatment strategy vs standard of care in patients admitted for acute decompensated HF *A*: Study effects of unblinded BVA results on provider treatment choices and clinical endpoints *B*: Develop a new BVA-guided treatment algorithm based on the observed experience with BVA at Duke

4. Design & Procedures

Perform a pragmatic randomized pilot study (N=50) with BVA- guided treatment strategy vs standard of care in patients admitted for acute decompensated HF.

The main intent for this pilot study is to gather information on optimal study design, treatment recommendations and sample size for a future planned pivotal trial.

Design: Pragmatic pilot study of patients admitted with acute HF. Upon enrollment patients will be randomized to either the unblinded arm (BVA- guided treatment), or blinded arm (Standard of care treatment), where BVA results will not be provided to patients or provider team. The study is planned to start in the Spring, 2020 and be open for enrollment for 1 year. (**Figure 2**)

Population: Patients presenting to Duke Hospital with a history of HF and worsening symptoms of HF will be enrolled in the study. Exclusion criteria are: Ongoing pregnancy, age <18 years, post heart transplantation or ongoing mechanical circulatory support, and end stage renal disease.

Treatment protocol: A pre-determined assortment of demographic and medical information will be gathered for all patients upon admission, 24h, 48h, 72h and upon completion of repeat BVA and upon discharge. See flow chart below (**Table 1**).

Table 1: Patient assessments during the study. SOC indicates standard of care and CS indicates clinical study related procedures.

Required Assessment	Baseline	Day 1	Day 2	Day 3	Day before discharge	Discharge	30 days post discharge
Consent/Randomization	X (CS)						
Medications	X (SOC)	X (SOC)	X (SOC)	X (SOC)	X (SOC)	X (SOC)	X (CS)
Vitals (BP, HR, RR, SpO2, weight)	X (SOC)	X (SOC)	X (SOC)	X (SOC)	X (SOC)	X (SOC)	
Orthostatic vitals	X (CS)				X (CS)	X (CS)	

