- Orthostatic heart rate and blood pressure (5 minutes supine, 1+5 minutes sitting and 1+5 minutes standing) on the day before procedure if the subject is an inpatient and again within 1 hour before procedure (CS). Also we will document whether subjects have symptoms bending over for 10 seconds (bendopnea).
- Non-invasive Testing
 - Fluid Lung Content measurement of chest fluid content using the ReDS[™] unit (Sensible Medical, Tenafly, NJ). The ReDS unit is a vest that emits radiofrequency waves to measures fluid content. The device is FDA approved. The measurement requires 10 minutes.
 - **Impedance** for lung water volume measure using the Cardioset which uses electrical impedance technique to determine intra-thoracic blood volume.
 - Arterial stiffness assessment (Pulse Wave Analysis): We will use the Sphygmocor[™] (AtCor Medical, Itasca, IL) to measure arterial stiffness. It is measured through a brachial cuff. This measurement requires 5 minutes.
- **Bedside ultrasound** will be performed of the heart and abdomen. We will assess: left ventricular function, inferior vena cava dimensions and collapsibility.

A phone call at 30 days will evaluate the vital status of the patient, potential changes in medications after discharge, and assess the patient's symptoms via the standardized questionnaires.

Physicians will be interviewed with a questionnaire at the time point of the BVA testing. The questionnaire will explore whether the unblinded BVA results changed the perception of the patients' congestion status and if they will result in a change in management.

Randomization process: Randomization will be performed by the study coordinator using computer software.

Potential complications:

 The radiation effective dose from a single administration of I-131 albumin for blood volume measurement is 0.60 mSv which is equal to three chest x-ray exams. It is equivalent to about 2 months of natural background exposure.

5. Selection of Subjects

For this study we seek to enroll heart failure patients admitted for acute decompensated heart failure to the cardiology service at the Duke Hospital. All patients irrespective of gender, race, and ethnicity will be considered for the study.

Exclusion criteria are:

- Ongoing pregnancy
- age <18 years
- Recent acute MI or hemodynamic instability: Acute MI (STEMI or Type I NSTEMI) within 7 days
- post heart transplantation or ongoing mechanical circulatory support
- Progressive cardiogenic shock

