- Patients with Ventricular Assist Devices
- End stage renal disease

6. Subject Recruitment & Compensation

Potential subjects will be identified via two potential pathways.

Inpatients will be identified within 24 h of the admission via screening of the admission logs and inpatient census. Consent process will occur in the subjects' hospital rooms on Duke Hospital Divisions 7700/7100/7300/7200/3100/3300/7 East.

Patients considered for this study will be identified within 24 h of admission. Prior to approaching the patient we will discuss the patient and his/her eligibility with the primary cardiology team. Study team will be introduced by the primary team. Ample time will be given to the patient to review the consent and have all questions answered. After the patient has consented to the study we will begin study related activities. The primary enrollment target is up to =50.

Subjects will be informed that their participation is strictly voluntary. They will be assured that the decision to decline participation will have no impact on their care or the perceptions of their providers.

The subject will be compensated \$100 for participation in this clinical study.

7. Consent Process

Candidate subjects will be informed of the risks and benefits of participation in the study. They will be informed of the study process and demands. They will be given a copy of the informed consent document to review and afforded adequate time to do so.

Informed consent will be obtained prior to the study. Consent will be obtained by the study Principal Investigator (PI), Duke Heart Center study coordinators who are trained on the study and who have been trained on the informed consent process, and other key personnel as designated by the PI. Consent will be obtained in the subjects' rooms. A subject is considered enrolled in this clinical study at the time at which the subject and investigator or authorized designee have personally signed and dated the Informed Consent Form.

8. Subject's Capacity to Give Legally Effective Consent

Subjects must to be able to understand the English language and understand the study process, including all potential risk and benefits. Any subject for whom the study personnel or treatment team has cause for concern regarding the subject's ability to understand the study process or follow the consent process, will be excluded from the study.

9. Study Interventions

- Lab draws
- Vital signs
- Orthostatic vital signs

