- Non-invasive imaging with ultrasound
- Non-invasive hemodynamic monitoring (heart rate variability, Sphygmocor ReDS,

Cardioset)

- Blood volume analysis

10. Risk/Benefit Assessment

This study is associated with only small risks and has the potential to provide significant insight into the physiology of the patient's congestion. Risks are limited to the intravenous line placement, and radiation exposure.

Anticipated benefits to the subject include detailed information on congestion status and extent of fluid overload, otherwise not captured with standard clinical care diagnostic methods. This newly obtained data will be provided back to the patient and provider which then can result in a change in clinical care. However the study or protocol does not have an influence on the clinical care the patient will receive as a result of the newly obtained information.

11. Costs to the Subject

Study-specific activities and assessments will be conducted at no additional cost to the subject. Subjects will still be responsible for standard of care procedures related to hospitalization for heart failure.

12. Data Analysis & Statistical Considerations

Descriptive statistics of continuous outcomes will include sample size, mean, median, standard deviation, minimum and maximum. For categorical outcomes, the number and percentage of subjects in each category will be presented. Statistical comparisons will be made using t-tests for continuous outcomes and chi square or Fisher's exact test (depending on overall event rates) for categorical outcomes.

13. Data & Safety Monitoring

Significant adverse events associated with the study procedures are not expected. 30 day follow-up is planned. Should complications be encountered, they will be reported to the IRB within 10 working days or per IRB policy. The Principal Investigator will also provide an annual report of any side effects or problems to the IRB during the study renewal process.

No protected health information associated with the study procedures will be sent outside of Duke. PHI (subject ID, height, weight, and gender) will be used internally for measuring the blood volume. Additionally, we will capture the birth year of the patient to perform the pulse wave analysis.

14. Privacy, Data Storage & Confidentiality -

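### Section 12 makes unadjusted significance tests the only between-arm inference, with no primary comparison, alpha, multiplicity approach or interval estimate, in a pilot meant to inform a pivotal trial.

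*Combined protocol and SAP*

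**What the plan says.** Section 12 has three sentences. The first covers continuous outcomes: "Descriptive statistics of continuous outcomes will include sample size, mean, median, standard deviation, minimum and maximum". The second promises counts and percentages for categorical outcomes. The third is the only inferential statement: "Statistical comparisons will be made using t-tests for continuous outcomes and chi square", with Fisher's exact test as the alternative for categorical outcomes, according to the event rates. It lists no outcomes or visits, and gives no alpha, no multiplicity approach and no interval. It also plans no between-arm difference as a reported quantity and no baseline adjustment.

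The rest of the document does not fill these gaps. Section 3 states Objective A as "Study effects of unblinded BVA results on provider treatment choices and clinical endpoints", without naming an endpoint. Section 4 gives the main intent as to "gather information on optimal study design, treatment recommendations and sample size for a future planned pivotal trial". The size is 50 in total (Section 4), and Section 6 says "The primary enrollment target is up to =50", so 50 is a ceiling. The allocation ratio is not stated; Section 4 says only "Randomization will be performed by the study coordinator using computer software". Table 1 schedules many assessments at up to six post-baseline time points.

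**The concern.** The stated purpose and the planned output do not match. A pilot that feeds a pivotal trial should yield estimates of differences, event rates or SDs, each with its uncertainty. Section 12 plans p-values, and gives its descriptive figures without precision. Nothing identifies which parameter the next trial will need.

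At this size a p-value is a poor guide. Because outcome and time point are left open, they can be chosen after the data are seen, and some tests may fall below 0.05 by chance. A real but modest effect will usually be missed, and when it does reach significance its estimate will be too large. If such a result were used to choose the pivotal endpoint or its assumed effect, the pivotal trial could be built on a chance finding or be too small.

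**Working it through.** The plan gives no derivation for N=50, so there is no figure to reproduce. The checks below use these inputs.

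- Total of 50 (Section 4). **Assumed:** 1:1 allocation, 25 per arm, all measured.
- **Assumed:** two-sided 0.05 per test, since no alpha is stated.
- Number of tests k: **not stated**, so three counts built from Table 1 are shown.

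**Counting.** Post-baseline cells per row are: vitals 5, orthostatic vitals 2, urine output 5, labs 3, BVA 1, dyspnea 6, impedance and lung fluid 2, echocardiogram 1, pulse wave 1, physician questionnaire 1, 30-day call 1.

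- One test per row, leaving out medications: k = 11.
- One test per row and visit: the cells sum to 28. Adding 6 for medications gives k = 34.
- Components split, without medications (5 vitals, 2 orthostatic measures, 4 lab items, 2 dyspnea scales, 2 lung-fluid devices): 25 + 4 + 5 + 12 + 1 + 12 + 4 + 1 + 1 + 1 + 1 = 67.

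**Chance of at least one false positive, no true effect.** For independent tests it is 1 − 0.95^k; for example, 1 − 0.95^34 = 0.825. For test statistics with a common correlation ρ it is 1 − ∫ φ(u) [Φ((1.96 − √ρ·u)/√(1−ρ)) − Φ((−1.96 − √ρ·u)/√(1−ρ))]^k du. The expected number of false positives is 0.05k at any correlation.

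| k | Expected | Independent | ρ = 0.5 | ρ = 0.7 | ρ = 0.9 |
|---|---|---|---|---|---|
| 11 | 0.55 | 43% | 30% | 22% | 13% |
| 34 | 1.7 | 83% | 53% | 35% | 18% |
| 67 | 3.35 | 97% | 69% | 44% | 21% |

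Independent tests first pass 50% at k = 14. A single pre-named test would carry 5%.

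**Power and exaggeration.** For a two-sample t-test with 48 df the critical value is 2.011. An observed difference must therefore reach 2.011 × √(2/25) = 0.57 SD to be significant, which is also the half-width of the 95% CI. With a true effect of 0.3 SD (illustrative), the non-centrality is 0.3 × √(25/2) = 1.06 and power is 18%. The significance threshold alone is 0.57/0.3 = 1.9 times the true effect. By simulation, the estimates that pass it average 2.35 times the true effect.

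**Precision of sample-size inputs.**

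- *Continuous endpoint.* The 95% limits for a pooled SD on 48 df are √(48/69.02) = 0.83 and √(48/30.75) = 1.25 times the estimate. Required N scales with SD², so it could range from 0.70 to 1.56 times the figure computed from the raw SD. The one-sided 80% upper limit is √(48/39.62) = 1.10 times the estimate.
- *Binary endpoint.* An observed 5/25 (20%, illustrative) has an exact 95% CI of 7% to 41%.

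**The case against.** The strongest reply is that this is a self-described pilot with no stated confirmatory claim. Section 12 commits to n, means, SDs, counts and percentages. If these are reported by arm, anyone can compute an unadjusted 95% CI for a difference, or a limit for an SD. A reader might infer that the pilot cannot serve its sample-size purpose; that does not follow. The precision is unplanned, not unobtainable. Sample size is also only one of three stated aims, and developing a treatment algorithm (Objective B) needs no test at all. This part of the reply stands. Nor is the lack of a power calculation an error in a pilot.

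A reader might also infer that every outcome is tested at every visit. Section 12 does not say so, and Table 1 schedules data collection, not analysis. Some cells are doubtful as between-arm tests. The physician questionnaire asks about the effect of unblinded results, which only the guided arm receives. Medications are not a single variable. Much of the 30-day call is already counted under medications and dyspnea. Splitting components pushes the count the other way. Each value of k is therefore a construct, which is why a range is shown.

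What the reply does not remove is that the choice of outcome and time point is open, that p-values are the only planned inference, and that no pivotal parameter is identified. Baseline-adjusted differences also cannot be recovered from the planned summaries; they need the patient-level data.

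**Conclusion.** The concern holds as a mismatch between purpose and planned analysis, and it should be corrected. Section 12 leaves the testing unrestricted and plans no between-arm estimate with its precision, although the pilot is meant to inform a pivotal trial.

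The size of the false-positive risk is uncertain, from 13% to 97% across the cases shown. It would be tempting to say that a false positive is probable. That is true for 34 or 67 tests at correlations up to 0.5, but not for 11 tests even if independent, nor for any of these counts at correlation 0.7 or above. Repeated measures in the same patient may well be strongly correlated. The firmer results are the 18% power and roughly 2.4-fold exaggeration at a true effect of 0.3 SD. These depend on 25 per arm, two-sided 0.05 and the illustrative effect, but not on the number of tests. The SD limits matter only if the pivotal endpoint is continuous. The outcomes that the Background uses to motivate guided care include rehospitalization and mortality, so the precision of an event rate may be what counts. That the team would choose its pivotal endpoint by p-value is a risk the plan leaves open, not something it states.

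**What to change.** Amend Section 12 in three places.

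1. Report each outcome as a between-arm difference with a 95% CI, adjusted for baseline where a baseline value is collected, in place of significance claims.
2. Name one primary comparison and time point in advance, chosen by the investigators, and label all others exploratory.
3. Report the precision of the parameters that the pivotal trial would use: a CI for event rates if its endpoint is binary, or a CI or upper limit for the SD if it is continuous.

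If a blood-volume measure is considered as primary, mean change in ml is a weak choice. The Background reports that about 34% of patients admitted with decompensated HF are hypovolemic or euvolemic, and Section 4 describes a patient-specific target. Guided care could thus move volume differently in different patients, and the mean could cancel out. A measure such as distance from the patient's own target would avoid this.

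The cost is a few sentences of SAP text and routine analysis, with no extra patients, visits or data. The downside is fewer claims of significance. It is a cheap improvement.
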